4.5. Visual Analog Scale (VAS)

The study subjects will be asked to complete a 10-point Visual Analog Scale (VAS) for the following assessments:

Level of pain and discomfort associated with study procedure – to be completed by the subjects on the day of the procedure, immediately following the procedure. Scoring will consist of making a mark on a 10-points scale. Each line will be awarded a score of 0 - 10 according to the level of pain when 0 is no pain and 10 is the maximum pain possible. See **שגיאה! מקור ההפניה לא נמצא.**

Additional patients' Reported Outcomes (PROs)

- Subject Subjective Downtime Assessment - Downtime defined as the period of time following the procedure during which the subject felt unable/unwilling to go out in public due to edema and/or erythema. The determination of "downtime" is measured in hours or days following the procedure. This will be recorded following every treatment visit (see **שגיאה! מקור ההפניה לא נמצא.**).
- Subject experience questionnaire will be filled by the subject at each follow-up visits (see **שגיאה! מקור ההפניה לא נמצא.**).

5 ADVERSE EVENTS ASSESSMENT AND REPORTING

5.1. Adverse Events Evaluation

Safety evaluation for this study includes an interview with the study subject at each visit by the Investigator or Research Coordinator to elicit information about any medical occurrence that meets the definition of Adverse Event. This information will be documented in CRF without regard for cause or relation to device and/or procedure. In addition, study subjects will be instructed to report all of complications experienced post study procedure to the site personnel as soon as they occur/are observed. It is the Investigator's responsibility to determine seriousness, severity, and relatedness of the Adverse Event to the device and procedure using the definitions below.

All adverse events, anticipated or unanticipated, will be monitored until they are adequately resolved or explained.

5.2. Reporting Requirements

All adverse events (AEs) observed by study subjects, investigators, or other study staff from first exposure to the study product through last study follow-up visit will be recorded. If a device related AE, SAE, or unanticipated serious device related effect is ongoing at the final study visit, the subject will be followed until resolution, until the condition stabilizes, until the event is otherwise explained, or the subject is lost to follow-up. The investigator should make every effort to ensure that follow-up includes any supplemental investigations as may be indicated to elucidate, as completely as practical, the nature and/or causality of the AE or SAE. This may include unscheduled follow up visits for AE assessment.

Study subjects will be instructed to report all AEs to the clinical study staff. AE information will be collected throughout the study and recorded on CRFs.

5.3. Contact email for SAE immediate reporting:

Study personnel must report to the sponsor any SAE or UADE by telephone as well as by email, as soon as possible and no later than 24 hours of the awareness of the event. The initial telephone notification (or email) should be followed by a written report (Serious Adverse Event report form) describing the SAE or UADE and signed by the investigator.

Study personnel must forward follow-up information and complete event report to the sponsor as the event continues and/or subsides/resolves, or in the case of permanent impairment, until the event stabilizes, and the overall clinical outcome has been ascertained. The SAE report (initial and/or follow up) should be sent via e-mail to the sponsor at [contact].

5.4. Severity of Adverse Events

The severity of adverse events will be categorized using the following criteria:

- **Mild:** easily tolerated by the subject, causing minimal discomfort and not interfering with everyday activities. These events generally do not require treatment.
- **Moderate:** sufficiently discomforting to interfere with normal everyday activities. These events are usually relieved by simple therapeutic measures.
- **Severe:** prevents normal, everyday activities. These events may require systemic drug therapy or other medical treatment.

5.5. Relationship to the Study Device and/or Procedure

Each AE should be assessed for its relationship to the device or procedure as identified as follows:

Device: This category should be restricted to adverse events directly attributable to the effect of the device.

Procedure: A procedure is any activity that supports the usage of the device.

Use the following categories for assigning the certainty of the relatedness:

Definitely Related: An AE is definitely related if it is obvious, certain or there is little doubt regarding the relationship.

Probably Related: An AE is probably related if cannot be explained by a concomitant illness or by other medicinal products.

Possibly Related: An AE is possibly related if it is capable of being related but relatively unlikely.

Not Related: An AE is not related if it is determined that there is no plausible association.

Unknown: Use this term if there is insufficient information to determine if the AE is related to the device or procedure.

5.6. End of Study

The end of study will be defined as completion of all study visits by all enrolled subjects. If a device-related AE, SAE, or unanticipated serious device-related effect is ongoing at the final study visit, the subject will be followed until resolution, until the condition stabilizes, until the event is otherwise explained, or the subject is lost to follow-up.

Study closure visits may be conducted at all clinical sites in order to review record retention requirements, device disposition requirements, etc., with site personnel. The Sponsor may choose to conduct the closure visit via telephone contact if appropriate.

5.6.1. Premature Termination or Suspension of the Study or a Study Site

Novoxel Clinical/RA department may terminate the participation of a center before the completion of the investigation due to one or more of the following reasons:

- The investigator is unable or unwilling to continue the investigation,
- The investigator is unable or unwilling to comply with the protocol requirements,
- The Monitoring audit results indicate study staff non-compliance.

The Sponsor may also terminate a study prematurely in case of:

- Safety concerns,
- Inability to obtain the number of subjects required by the protocol,
- Any other reason, pre-defined within the protocol.

5.7. Audits / Inspections

The Sponsor, their designee, and the reviewing IRB may monitor or audit the study centers. Likewise, regulatory authorities may inspect Sponsor or study vendors/CRO files or any study center to evaluate the conduct of the study. The Investigator must allow access to the subject files and inspection of their clinical research protocol procedures when requested.

6 STATISTICAL METHODOLOGY

This section describes the statistical analyses foreseen at the time of study planning. Any deviations from planned analyses, the reasons for such deviation, and all alternative or additional statistical analyses that may be performed before database close will be summarized in the Clinical Study Report.

6.1. Determination of Sample Size

- The objective of this study is to demonstrate that study participants positively respond to the Tixel, thus the primary endpoint will be assessed via the percentage of study participants that demonstrated an improvement in the FWCS from baseline to the 3-month visit.
- An improvement is clinically important when FWCS ≥ 1 score.

The sample size calculation is based on the rate of subjects for which a score improvement on the FWCS at 3-month compared to baseline (success rate). The success rate is expected to be 65%.

When the sample size is 44, a two-sided 95% confidence interval for a single proportion using the large sample normal approximation will extend 0.14 from the observed proportion for an expected proportion of 0.65.

To account for possible missing data (up to 15% attrition), 51 subjects will be enrolled.

- Total N: up to 51 study participants

A study investigating the effects of RF device on the improvement of appearance of peri-orbital wrinkles (VIVACE K150409 Class II FDA approved device) utilized a FWCS cutoff as 60%, supporting this value in the present sample size computation.

6.2. Analysis Sets

The full analysis set (FAS) will be used for analysis of safety parameters and secondary endpoints in this study.

6.2.1. Full Analysis Set (FAS)

All subjects enrolled in the study who received at least one treatment, will be included in the FAS.

6.2.2. Per Protocol Set (PPS)

The PPS is the subset of subjects in the FAS without major protocol deviations and only if received the full treatments and have quality photos in the baseline and in the 3 months follow-up visit. Major protocol deviations will be decided and finalized by an independent reviewer prior to database lock. The primary efficacy analyses and also the secondary efficacy endpoints (in addition to the FAS) will be analyzed on the PP population.

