1.7. Study Endpoints

1.7.1. Primary Efficacy Endpoint

Comparison of the proportion of subjects with a ≥ 1 -score improvement on the FWCS at the 3-month visit compared to baseline as determined by at least 2 out of 3 blinded Independent Photographic Reviewers.

The study design assumes a 65% success rate of subjects with a ≥ 1 -score change on the FWCS, therefore, greater or equal to 65% of subjects must be rated with a ≥ 1 -score improvement 3 months after treatment and must be statistically significantly.

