4.2. Fitzpatrick Wrinkle Classification Scale (FWCS)

Assessment of subject wrinkles will be performed by the Investigator and in addition, will be performed by three board-certified independent dermatologists or plastic surgeons ("Raters"), using the Fitzpatrick Wrinkle Classification Scale (FWCS) categories as shown in Table 4. The FWCS is a clinically validated assessment tool used to assess skin wrinkle severity and elastosis on a scale from 1 through 9, where the lower score is considered better.

The investigator will assess FWCS at baseline, 1-months and 3 months follow up visit, while the raters will assess only at baseline and 3 months follow up visit.

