4.3. Blinded Identification of 3-Month Images

Assessment of each subject's baseline and 3-month follow-up images viewed simultaneously will be performed by the Independent Photographic Reviewers ("Raters") who will be blinded to the study subject's visit (baseline and 3-month follow-up visit). Each rater will view each subject's randomized baseline and 3-month follow-up images and assess which set of images represent the subject's post-treatment images. Each photograph will have a unique identification number, but the sets of images will not be arranged in any specific order. The Raters will assign a single FWCS score per subject at each time point. A subject will be considered a success if at least 2 out of the 3 Raters correctly identify the 3-month images and the FWCS score is ≥ 1 .

Table 4- Fitzpatrick Wrinkle and Elastosis Scale

Class	Description	Score	Description
I	Fine wrinkles	1-3	Mild: Fine texture changes with subtly accentuated skin lines.
II	Fine to moderate depth wrinkles, Moderate number of lines	4-6	Moderate: Distinct papular elastosis (individual papules with yellow translucency under direct lighting) and dyschromia
III	Fine to deep wrinkles, numerous lines, with or without redundant skin folds	7-9	Severe: Multipapular and confluent elastosis (thickened, yellow, and pallid) approaching or consistent with cutis rhomboidalis.

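### The primary responder analysis is placed on the per-protocol set, and no full-analysis-set version is defined to show whether exclusions have raised the rate judged against 65%

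*Combined protocol and SAP*

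**What the plan says.** Three parts of Section 6 bear on which subjects enter the primary analysis.

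- Section 6.2: "The full analysis set (FAS) will be used for analysis of safety parameters and secondary endpoints in this study". The primary endpoint is not listed.
- Section 6.2.1: "All subjects enrolled in the study who received at least one treatment, will be included in the FAS".
- Section 6.2.2: "The primary efficacy analyses and also the secondary efficacy endpoints (in addition to the FAS) will be analyzed on the PP population". Members of this set must have no major deviation and qualify "only if received the full treatments and have quality photos in the baseline and in the 3 months follow-up visit". On deviations it adds: "Major protocol deviations will be decided and finalized by an independent reviewer prior to database lock".

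Section 6.3.1 sets the bar at 65% of subjects and names no analysis set. Section 1.7.1 also asks for significance ("3 months after treatment and must be statistically significantly") but gives no null value.

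Section 4.3 ties success to the images: "A subject will be considered a success if at least 2 out of the 3 Raters correctly identify the 3-month images". Section 4.2 says when scores are taken: the investigator also scores at one month, "while the raters will assess only at baseline and 3 months follow up visit".

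Section 6.4.3 offers three ways of handling a missing month-3 FWCS score: the mean for that evaluator, the subject's baseline score from that evaluator, and an MMRM on all enrolled subjects. It promises sensitivity analyses of the imputation. It does not say which method serves the primary endpoint, or how a subject with no month-3 photos is classed.

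**The concern.** Apart from the baseline photo, membership of the PPS is settled after treatment starts. A subject who stops early, misses the month-3 visit or has a major deviation leaves both numerator and denominator. With no control arm, there is no second group in which similar exclusions might offset the effect, and the observed rate is compared directly with a fixed number.

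If those who drop out respond less often than those who stay, the PPS rate is higher than the rate among treated subjects, and the choice of set alone could decide whether the 65% point bar is met. The plan defines no direct check on the primary endpoint. The FAS secondary analyses use the treating physician's own FWCS, which is indirect evidence about a blinded photographic endpoint. An MMRM of scores does not by itself give a two-of-three-rater proportion, and it has no interim rater score to draw on.

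**Working it through.** **Inputs from the documents.** Section 6.1: 44 evaluable subjects, expected rate 0.65, up to 15% attrition, 51 enrolled. Section 6.3.1: point bar of 65%.

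**Inputs that are assumptions.** The number outside the PPS is taken as 51 − 44 = 7 (13.7% of 51). The documents give only an upper figure for attrition; exclusions for deviations or photo quality could add to it, and actual losses could be smaller. All 51 are first taken as treated. The response rate among excluded subjects is varied, because the documents give none.

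1. **The plan's own figures.** The half-width is 1.96 × √(0.65 × 0.35 / 44) = 0.141, which agrees with the stated 0.14. Inflation: 44 × 1.15 = 50.6, rounded up to 51, as stated. (Dividing by 0.85 would give 51.8, or 52; the difference does not matter here.)

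2. **A bare pass on the PPS.** The smallest count reaching 65% of 44 is 29 (29/44 = 65.9%).

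3. **The same result on the FAS.** The rate is (29 + 7r)/51, where r is the response rate among the excluded:
   - r = 0: 29/51 = 56.9%
   - r = 0.40: 31.8/51 = 62.4%
   - r = 29/44: 65.9%, no overstatement

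   The FAS reaches the bar at 34/51 = 66.7% (33/51 = 64.7% falls short), so at least 5 of the 7 must respond.

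4. **If 2 of the 7 were never treated.** The FAS is then 49. With no response among the other 5, the rate is 29/49 = 59.2%. The bar is 32/49 = 65.3%, so 3 of the 5 must respond.

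5. **Fewer exclusions.** With 5 outside the PPS, 30/46 = 65.2% becomes 30/51 = 58.8% (none respond) or 32/51 = 62.7% (40%). With 3 outside, 32/48 = 66.7% becomes 32/51 = 62.7% or 33.2/51 = 65.1%.

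6. **Chance of meeting the point bar** (exact binomial, true PPS rate 65%, 7 excluded). On the PPS, P(X ≥ 29 of 44) = 51.9%. On the FAS of 51 it is 5.7%, 27.2% or 46.5% when the excluded respond at 0, 40% or 65%. The remaining gap at equal response is only integer rounding of the bar. With a FAS of 49 and no response among the excluded it is 18.0%.

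7. **The significance condition.** It is set aside above because no null is stated. Against an assumed null of 60% (exact, one-sided 2.5%), the PPS needs 34/44 and the FAS 38/51. At a true 65% throughout, the chances are 5.7% and 9.9%, so under equal response the larger set does better.

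**The case against.** The strongest reply rests on Section 6.4.3. It seeks month-3 scores from everyone enrolled and imputes evaluator by evaluator. Replacing a rater's missing score with that rater's baseline score gives zero change, so a non-responder classification follows mechanically. Since PPS entry requires month-3 photos, these rules would have little use unless a wider set were analysed. The FAS parenthesis in Section 6.2.2 can also be read to cover the primary endpoint. This largely stands: a reader might infer that the plan has no analysis beyond the PPS, and the text does not support that. What remains is that no section links the wider analysis to the primary proportion, and that Sections 6.2, 6.2.2 and 6.4.3 are not reconciled.

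The size of any effect is also unknown. The lowest figures need zero response in every excluded subject, and some exclusions, such as a poor baseline photo, have no evident link to response. That is correct, and it is why the claim is conditional.

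Finally, deviations are settled by an independent reviewer before database lock. This is a real safeguard, and nothing in the documents shows that exclusions would be made with knowledge of the ratings. But the plan does not say who judges photo quality or whether rater scores exist by then. Footnote c to Table 2 places blinded assessment after the subject's activities are complete, which does not settle the order. Exclusions made blind can still bias the rate.

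**Conclusion.** The concern holds in a conditional form. Read together, Sections 6.2 and 6.2.2 put the primary responder analysis on the PPS, and no FAS version of that proportion is defined. With 7 of 51 treated subjects excluded, a bare PPS pass of 65.9% corresponds to anything from 56.9% to 65.9% on the FAS as response among the excluded runs from none to equal. The lower end is 59.2% if 2 of the 7 were untreated. If excluded subjects responded more often, the bias would reverse.

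Two stronger readings are not supported. One is that the PPS rate will be inflated: the documents give neither the number excluded nor their response. The other is that the FAS must be the sole primary analysis. That is defensible, but it materially changes the chance of passing a design built on 44 evaluable subjects, and it is the sponsor's decision. The defect that needs correcting before data are seen is the missing specification, because a FAS analysis or non-responder rule added later would be post hoc.

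**What to change.** In Sections 6.2, 6.2.2 and 6.4.3:

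- Pre-specify a FAS analysis of the primary responder proportion, report it beside the PPS result, and require the conclusion to address both.
- Use every available month-3 photo, whether or not all treatments were completed. Table 2 times Visit 6 only from the fourth treatment, so the plan should say when photos are due for a subject who does not reach it.
- Class treated subjects with missing or unusable month-3 photos as non-responders. This follows from the plan's own baseline-value imputation applied rater by rater.
- Label mean imputation and the MMRM as sensitivity analyses.
- Report unusable baseline photos separately, with a sensitivity analysis. Do not count them as treatment failures: the fault arises before treatment, and neither Section 4.3 nor Section 6.4.3 covers it.
- Fix deviation and photo-quality decisions before any rater score is available.

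The change is mainly wording and needs no extra subjects for precision: the half-width at 65% is 0.131 with 51 subjects against 0.141 with 44. The cost is a possibly lower rate. If all 7 losses count as failures, meeting 65% on the FAS takes 34 responders among the 44 PPS subjects (34/44 = 77.3%). At a true PPS rate of 75%, the chance of meeting the point bar is then 44.2% on the FAS against 93.7% on the PPS. The FAS figure rises to 77.0% if the excluded respond at 40% and 93.4% if they respond at 75%. If the sponsor makes the FAS primary, the sample size or the bar should be revisited with these figures in view, and the null value stated.

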6.3. Endpoints for Analysis

6.3.1. Primary Efficacy Endpoint

The primary efficacy endpoint is the comparison of the proportion of subjects (i.e. percentage of treatment responders) with a ≥ 1 -score improvement on the FWCS at the 3- month visit, as compared to baseline as determined by at least 2 out of 3 blinded Independent Photographic Reviewers. The study design assumes a 65% success rate of subjects with treated wrinkles with a ≥ 1 -score change on the FWCS; therefore, even or greater than 65% of subjects must be rated with a ≥ 1 -score improvement 3 months after treatment. and must be statistically significantly.

6.3.2. Secondary Efficacy Endpoint

shall be assessed and quantified by the handling physician.

The following assessment methods will be applied (frontal clinical assessment or by images):

- FWCS - Fitzpatrick Wrinkle Classification Scale (at each FU visit)
- GAIS - Global Aesthetic Improvement Scale Assessment (at each FU visit)

Patients' Reported Outcomes (PROs):

- Subject Experience and Satisfaction Questionnaire (in the 2 FU visits)
- Subject Subjective Downtime Assessment (following each treatment visit)

6.4. Statistical Analysis for Safety Variables

6.4.1. Primary Safety Variable

The primary safety variable is the evaluation of adverse events up to the 3-month visit after treatment. Adverse events reported at each scheduled study visit will be summarized. A descriptive analysis including type, onset after treatment, duration, severity, and relationship to study device and/or procedure will be provided.

6.4.2. Secondary Safety Variables

6.4.2.1. Visual Analog Scale (VAS)

Evaluation of the pain and discomfort of the treatment as reported by the subject on a 10-point visual analog scale (VAS). Results of the VAS on a scale of 0 (no pain) to 10 (most severe pain) will be summarized descriptively utilizing mean, standard deviation, minimum, maximum, median, and the 95% confidence interval of the mean.

6.4.2.1.1. Subject Downtime Assessment

Downtime defined as the period of time following the procedure during which the subject felt unable/unwilling to go out in public due to edema and/or erythema. The determination of “downtime” is measured in hours or days following the procedure. This will be recorded following each treatment visit. See appendix D.

6.4.3. Handling of Missing Data

- Every effort will be made to obtain all FWCS data at month-3 evaluation from all subjects who have been enrolled to minimize missing data. However, in the event when there is missing data the following imputation methods will be used.
- Imputation using mean values: the missing FWCS value will be replaced by the average of non-missing FWCS values at month-3 in the same treatment group by the same evaluator.
- Imputation using baseline values: the missing FWCS value will be replaced by the subject's baseline FWCS value by the same evaluator.
- The MMRM model (Mixed-effect Model for Repeated Measures), which is based on MAR (missing at random) assumption will be applied to all enrolled subjects.

Sensitivity analyses will be applied for testing the effect of the imputation on the treatment effect. This will show the influence of the imputation on the study results.

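### The mean-value rule in 6.4.3 lets the baseline score alone decide response for subjects with no month-3 ratings, so it should not feed any responder rate

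*Combined protocol and SAP*

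**What the plan says.** Section 6.4.3 lists three approaches to a missing month-3 FWCS value.

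- Mean value: "the missing FWCS value will be replaced by the average of non-missing FWCS values at month-3 in the same treatment group", taken within evaluator.
- Baseline value: "the missing FWCS value will be replaced by the subject's baseline FWCS value by the same evaluator".
- An MMRM, "which is based on MAR (missing at random) assumption will be applied to all enrolled subjects".

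It then promises a comparison without describing it: "Sensitivity analyses will be applied for testing the effect of the imputation on the treatment effect". It does not say which analysis the imputed scores enter.

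The surrounding sections fix the context. Section 1.5 describes a single-arm study. Section 6.3.1 defines response as an improvement of at least 1 point according to at least 2 of 3 blinded raters. Section 4.3 adds an identification condition: "A subject will be considered a success if at least 2 out of the 3 Raters correctly identify the 3-month images". Section 6.2.2 places the primary analysis on the per-protocol set (PPS), which admits subjects "only if received the full treatments and have quality photos in the baseline and in the 3 months follow-up visit". Section 6.2 gives the full analysis set (FAS) another role: "The full analysis set (FAS) will be used for analysis of safety parameters and secondary endpoints in this study". The FAS itself is broad: "All subjects enrolled in the study who received at least one treatment, will be included in the FAS".

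**The concern.** The responder endpoint is a within-subject change turned into yes or no. Replacing a missing follow-up score by a group average does not respect that. With one arm, the same treatment group means everyone, so all subjects missing a given rater's score get one identical month-3 value. For a subject missing all three raters' scores, imputed response then separates high baselines from low ones and reflects nothing that happened after treatment. A subject with no 3-month images could be credited with a qualifying score change, although under section 4.3 such a subject cannot be a success.

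What is at stake is the check on the primary result. The PPS drops treated subjects who did not receive all treatments or lack usable photographs. A responder rate that puts treated subjects back is the natural way to see whether that restriction flatters the result. If it were produced under 6.4.3 as written, the mean-value rule could credit successes to subjects whose outcome nobody saw.

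**Working it through.** **The plan's own figures.** Section 6.1 gives 44 evaluable subjects, an expected rate of 65%, and 51 enrolled. The half-width is 1.96 × √(0.65 × 0.35 / 44) = 0.141, which agrees with the stated 0.14. For attrition, 44 × 1.15 = 50.6, rounded up to 51 (dividing, 44 / 0.85 = 51.8, gives 52). The plan's split is therefore 44 observed and 51 − 44 = 7 missing.

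**What the mean-value rule does.** Let m be a rater's month-3 mean among observed subjects. Imputed improvement is baseline − m, so imputed response means baseline ≥ m + 1. With m = 4.5 (assumed):

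| Baseline | 3 | 4 | 5 | 6 | 7 |
|---|---|---|---|---|---|
| Imputed improvement | −1.5 | −0.5 | 0.5 | 1.5 | 2.5 |
| Responder | no | no | no | yes | yes |

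Under the baseline-value rule the imputed change is always 0, so the subject is always a non-responder.

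**How often the mean-value rule creates a responder.** The documents give no distribution of rater baseline scores. The assumption is scores of 3–7 (the investigator's eligibility range in section 2.1) in three shapes: uniform; weights 0.1, 0.2, 0.4, 0.2, 0.1; and weights 0.1, 0.15, 0.25, 0.3, 0.2. The mean m is sampled from 44 subjects, with 100,000 simulated runs per case.

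| Mean change | Raters agree fully | Independent raters, 2-of-3 vote |
|---|---|---|
| None | 0.304 / 0.206 / 0.211 | 0.222 / 0.109 / 0.114 |
| 1-point fall | 0.504 / 0.512 / 0.509 | 0.507 / 0.517 / 0.513 |

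The columns are linked by the vote formula 3p² − 2p³: for p = 0.304 this is 0.277 − 0.056 = 0.221, matching 0.222 within simulation error. Raters see the same photographs, so reality lies between the columns.

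**Effect on a rate out of 51.** Assume 29/44 (65.9%) observed responders and 7 treated subjects missing all raters' scores. The expected rate is (29 + 7 × share) / 51.

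| Rule | Expected responders | Rate |
|---|---|---|
| Baseline value | 29 | 56.9% |
| Mean value, no mean change | 29 + 7 × 0.109 = 29.76 to 29 + 7 × 0.304 = 31.13 | 58.4% to 61.0% |
| Mean value, 1-point fall | 29 + 7 × 0.504 = 32.53 to 29 + 7 × 0.517 = 32.62 | 63.8% to 64.0% |
| Mean value, all 7 imputed as responders | 36 | 70.6% |

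Reaching 65% of 51 needs 34 responders (0.65 × 51 = 33.15; 33/51 = 64.7%, 34/51 = 66.7%), so 5 of the 7 must be imputed as responders. Treating missing subjects as independent with the shares above, that chance is about 23–26% with a 1-point fall and at most about 3% with no mean change.

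The no-change case sits awkwardly with 29/44 responders. If 29 subjects each improve by at least 1 point, the other 15 must worsen by at least 29/15 = 1.9 points on average to offset them. The 1-point fall is the more coherent illustration.

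**The case against.** The strongest reply is that the harm falls on an analysis the plan does not contain. The primary analysis is on the PPS, which requires month-3 photographs, and the FAS is reserved for safety and secondary endpoints. Section 6.4.3 imputes scores and never says that they enter the 2-of-3 responder rule; the obvious planned use is the investigator's FWCS, a secondary endpoint. Section 4.3 would also already make a subject without images a failure. The plural wording may mean that all three methods will be reported and compared.

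Most of this stands, and it limits the point. A reader might infer that the mean-value rule inflates the primary result; the PPS definition does not support that. A reader might infer that it would lift a failing rate past 65%; the expected rates stay below 65%, and 70.6% is an extreme. The missing label for a main method, and the MMRM's reference to all enrolled subjects, could be read as serious defects. They are missing detail with little effect: enrolment and first treatment both belong to Visit 1, whose two parts may be at most 7 days apart.

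What remains is that 6.4.3 states a concrete rule that is wrong for a responder endpoint and does not exclude that use. The identification condition in 4.3 would block it, but section 6.3.1 omits that condition, so the text does not settle the matter. The promised sensitivity analyses are not described.

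**Conclusion.** The point holds in limited form. Mean-value imputation is unsuitable for any responder analysis in this single-arm study: for a subject missing all raters' scores, baseline alone decides the outcome once the mean is fixed. If only one rater's score is missing, the two observed scores also count and the problem is smaller.

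On the illustrative data, the mean-value rule adds about 1.5 to 4 percentage points over the baseline-value rule with no mean change (58.4 − 56.9 to 61.0 − 56.9) and about 7 with a 1-point fall (64.0 − 56.9 = 7.1). These figures rest on assumed rater baselines, on 29/44 observed responders, and on all 7 missing subjects having been treated but lacking every month-3 rating. Section 6.1 gives 15% attrition as a ceiling, so the number missing may be smaller. The PPS primary result is essentially untouched.

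**What to change.** In section 6.4.3:

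1. State that mean-value imputation is not used for any responder analysis.
2. Add a supportive FAS analysis of the primary responder endpoint, reported beside the PPS result. Observed ratings are kept; missing ones follow the plan's existing baseline-value rule, so a subject with none is a non-responder.
3. Specify the promised sensitivity analysis as a tipping-point table that counts 0, 1, and so on up to all missing subjects as responders.

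As a minor clarification, state that the MMRM applies to the investigator's mean FWCS change on the FAS. Section 4.2 gives the investigator two follow-up assessments and the raters only one.

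The cost is wording and one table, with no new data. The drawback is that the supportive rate is conservative by construction. A true 65% in 44 observed subjects becomes an expected 0.65 × 44 / 51 = 56.1%, and the chance of at least 34 responders among the 44 (binomial, p = 0.65) is 5.7%. It should therefore support the PPS result and not replace it or be held to the 65% criterion.
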